6.0 Registration/Randomization Procedures

6.1 To register a patient, access the Mayo Clinic Cancer Center (MCCC) web page and enter the registration/randomization application. The registration/randomization application is available 24 hours a day, 7 days a week. Back up and/or system support contact information is available on the Web site. If unable to access the Web site, call the MCCC Registration Office at [REDACTED] between the hours of 8 a.m. and 4:30 p.m. Central Time (Monday through Friday).

The instructions for the registration/randomization application are available on the MCCC web page [REDACTED] and detail the process for completing and confirming patient registration. Prior to initiation of protocol treatment, this process must be completed in its entirety and a MCCC subject ID number must be available as noted in the instructions. It is the responsibility of the individual registering the patient to confirm the process has been successfully completed prior to release of the study agent. Patient registration via the registration/randomization application can be confirmed in any of the following ways:

- Contact the MCCC Registration Office [REDACTED] If the patient was fully registered, the MCCC Registration Office staff can access the information from the centralized database and confirm the registration.
- Refer to “Instructions for Remote Registration” in section “Finding/Displaying Information about A Registered Subject.”

6.2 Correlative Research

A mandatory correlative research component is part of this study, the patient will be automatically registered onto this component (see Sections 3.19c and 14.0).

6.3 Documentation of IRB approval must be on file in the Registration Office before an investigator may register any patients.

In addition to submitting initial IRB approval documents, ongoing IRB approval documentation must be on file (no less than annually) at the Registration Office [REDACTED] [REDACTED] If the necessary documentation is not submitted in advance of attempting patient registration, the registration will not be accepted and the patient may not be enrolled in the protocol until the situation is resolved.

When the study has been permanently closed to patient enrollment, submission of annual IRB approvals to the Registration Office is no longer necessary.

6.4 Prior to accepting the registration, registration application will verify the following:

- IRB approval at the registering institution
- Patient eligibility
- Existence of a signed consent form

- Existence of a signed authorization for use and disclosure of protected health information

6.5 At the time of registration, the following will be recorded:

- Patient has/not given permission to store and use his/her sample(s) for future research of Myelofibrosis at Mayo.
- Patient has/not given permission to store and use his/her sample(s) for future research to learn, prevent, or treat other health problems.
- Patient has/not given permission for MCCC to give his/her sample(s) to researchers at other institutions.

6.6 Treatment cannot begin prior to registration and must begin \leq 14 days after registration.

6.7 Pretreatment tests/procedures (see Section 4.0) must be completed within the guidelines specified on the test schedule.

6.8 All required baseline symptoms (see Section 10.51) must be documented and graded.

6.9 Treatment on this protocol must commence at Mayo Clinic Arizona under the supervision of a hematologist or healthcare professional.

6.9a Study drug is available on site.

6.9b Patient questionnaire booklet is available on site; copies are not acceptable for this submission.

7.0 Protocol Treatment

7.1 Treatment Schedule (Both Cohorts)

Dose level	Agent	Dose	Route	Day
-2	P1101	50 micrograms (mcg)	SQ	Day 1
-1	P1101	50 micrograms (mcg)	SQ	Day 1 and 15
0*	P1101	100 micrograms (mcg)	SQ	Day 1 and 15
1	P1101	150 micrograms (mcg)	SQ	Day 1 and 15
2	P1101	200 micrograms (mcg)	SQ	Day 1 and 15
3	P1101	250 micrograms (mcg)	SQ	Day 1 and 15
4	P1101	300 micrograms (mcg)	SQ	Day 1 and 15

*starting dose level

7.2 **All patients will be started at dose level 0 every other week, and then dose will be titrated up by 50mcg increments to a maximum dose of 300mcg every other week as**

tolerated.

7.3 Patients can be instructed in administration techniques and granted treatment independence with nursing staff approval. Patients should complete the Medication Diary (Appendix II) and be instructed to complete the Transfusion Diary (Appendix V).

7.3 For this protocol, the patient must return to the consenting institution for evaluation at least every 4 weeks during treatment through cycle 3 day 1, and then will return every 3 cycles.

7.5 Local Medical Doctor (LMD) treatment:
After cycle 3, day 1 and if the patient is tolerating therapy without excessive toxicity at a stable dose level, the patient may be seen by their Local Medical Doctor (LMD). Patients will need to return to Mayo Clinic Arizona at least every 3 cycles for assessment (refer to Section 4.0). The registering physician retains responsibility for the patient.

In this case, a written statement outlining drug dosage, method of administration, follow-up tests required, and telephone number to call to discuss any questions with the responsible investigator must be sent with the patient to provide necessary information to the LMD.

8.0 Dosage Modification Based on Adverse Events

Treatment modifications are based on adverse events. All adverse events should be graded according to the CTEP Common Terminology Criteria for Adverse Events (CTCAE v4.0). Dose modification recommendations listed below are general guidelines, and appropriate dose adjustments for patient safety should be done as deemed necessary by the treating physician or his representative.

ALERT: *ADR reporting may be required for some adverse events (See Section 10)*

Dose Modifications for P1101 (Based on Adverse Events in Tables 8.2)

Starting Dose	Dose level -1	Dose level -2	Dose level -3	Dose level -4	Dose level -5	Dose level -6	Dose level -7
100 micrograms (mcg)	50 micrograms (mcg) Days 1 and 15	50 micrograms (mcg) Day 1 only	Discontinue				
150 micrograms (mcg)	100 micrograms (mcg)	50 micrograms (mcg) Days 1 and 15	50 micrograms (mcg) Day 1 only	Discontinue			
200 micrograms (mcg)	150 micrograms (mcg)	100 micrograms (mcg)	50 micrograms (mcg) Days 1 and 15	50 micrograms (mcg) Day 1 only	Discontinue		
250 micrograms (mcg)	200 micrograms (mcg)	150 micrograms (mcg)	100 micrograms (mcg)	50 micrograms (mcg) Days 1 and 15	50 micrograms (mcg) Day 1 only	Discontinue	
300 micrograms (mcg)	250 micrograms (mcg)	200 micrograms (mcg)	150 micrograms (mcg)	100 micrograms (mcg)	50 micrograms (mcg) Days 1 and 15	50 micrograms (mcg) Day 1 only	Discontinue

Table 8.2: Dose modification guidelines for P1101 related adverse events (with an attribution of possible, probable or definite)

→ → Use the NCI Common Terminology Criteria for Adverse Events (CTCAE) version 4.0* unless otherwise specified ← ←

CTCAE System/Organ/Class (SOC)	ADVERSE EVENT	AGENT	ACTION**
BASED ON INTERVAL ADVERSE EVENT PRIOR TO DAY 15 EACH CYCLE			
Investigations	Grade 3 Platelet count decreased	P1101	Omit Day 15 treatment until platelet count resolves to grade 2 or less. Treatment may be restarted at the next lower dose level
	Grade 4 Neutrophil count decreased	P1101	Omit Day 15 treatment until neutrophil count resolves to grade 2 or less. Treatment may be restarted at the next lower dose level
	Grade 3 Alanine aminotransferase (ALT) increased	P1101	Omit Day 15 treatment until ALT resolves to grade 2 or less. Treatment may be restarted at the next lower dose level
	Grade 3 Aspartate aminotransferase (AST) increased	P1101	Omit Day 15 treatment until AST resolves to grade 2 or less. Treatment may be restarted at the next lower dose level
Non Hematologic	All other Non-Hematologic Toxicities Grade ≥ 3 (With the exception of nausea, vomiting or diarrhea controlled with appropriate medications.)	P1101	Omit Day 15 treatment and re-check weekly, when returns to \leq grade 2 resume treatment at next lower dose level.
AT TIME OF RETREATMENT ON DAY 1 OF EACH CYCLE			
Investigations	Grade 3 Platelet count decreased	P1101	Hold treatment until platelet count resolves to grade 2 or less, checking labs weekly. Treatment may be restarted at the next lower dose level. Contact study chair if treatment is held beyond 28 days.
	Grade 4 Neutrophil count decreased	P1101	Hold treatment until neutrophil count resolves to grade 2 or less, checking labs weekly. Treatment may be restarted at the next lower dose level. Contact study chair if treatment is held beyond 28 days.

CTCAE System/Organ/Class (SOC)	ADVERSE EVENT	AGENT	ACTION**
	Grade 3 Alanine aminotransferase (ALT) increased	P1101	Hold treatment until ALT resolves to grade 2 or less, checking labs weekly. Treatment may be restarted at the next lower dose level. Contact study chair if treatment is held beyond 28 days.
	Grade 3 Aspartate aminotransferase (AST) increased	P1101	Hold treatment until AST resolves to grade 2 or less, checking labs weekly. Treatment may be restarted at the next lower dose level. Contact study chair if treatment is held beyond 28 days.
Non Hematologic	All other Non-Hematologic Toxicities Grade \geq 3 (With the exception of nausea, vomiting or diarrhea controlled with appropriate medications.)	P1101	Hold treatment and re-check weekly, when returns to \leq grade 2 resume treatment at next lower dose level.

* Located at [REDACTED]

** Use the following to describe actions in the Action column:

- Omit = The current dose(s) for the specified drug(s) during a cycle is skipped. The patient does not make up the omitted dose(s) at a later time
- Hold/Delay = The current dose(s) of all drugs during a cycle is delayed. The patient does make up the delayed dose(s) when the patient meets the protocol criteria to restart drugs.
- Discontinue = The specified drug(s) are totally stopped.

NOTE: If the patient experiences a significant adverse event requiring a dose reduction at the start of the next cycle, then the dose will remain lowered for that entire subsequent cycle. If that cycle is completed with no further adverse events $>$ Grade 2, then the dose may be increased, at the investigator's discretion, one level at a time, in the following cycles.

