4.0 Test Schedule

Cycle = 28 days

Parameter	Prior to Registration ≤14 days	Active Monitoring					
		Cycle 1 Day 1	Cycle 1 Days 8, 15, 22 ±2 days	Cycle 2 and Cycle 3 Day 15	Prior to Treatment Cycle 2 Day 1 and Beyond	Prior to Treatment Cycles 2, 3, 6, 9 & 12 and every 3 cycles thereafter Day 1 ±3 days	At Treatment Discontinuation ±7 days
Medical History	X						
Prior Diagnosis/Prior Treatment	X						
Height (pre-study only)	X						
Weight, ECOG PS	X					X	X
Physical Examination	X					X	X
Serum pregnancy test(HCG) ³	X						
Vital Signs	X	X ⁷				X	X
CBC with Differential and peripheral blood smear (Can be from home lab for interval monitoring)	X		X ⁷	X ⁷	X ²		X
Chemistries (Sodium, potassium, creatinine, chloride, SGOT (AST), SGPT (ALT), Alkaline Phosphatase, Total bilirubin, glucose)	X		X ⁷	X ⁷	X ²		X
JAK2, BCR-ABL, CALR, & MPL	X ⁶					X ⁶	
Treatment Evaluation (see Section 11)						X	X
EKG	X						
Transfusion Assessment	X				X ⁵	X	X
Symptom Assessment Package (Patient Questionnaire Booklet)	X					X ¹	X

Parameter	Prior to Registration	Active Monitoring					
	≤ 14 days	Cycle 1 Day 1	Cycle 1 Days 8, 15, 22 ± 2 days	Cycle 2 and Cycle 3 Day 15	Prior to Treatment Cycle 2 Day 1 and Beyond	Prior to Treatment Cycles 2, 3, 6, 9 & 12 and every 3 cycles thereafter Day 1 ± 3 days	At Treatment Discon- tinuation ± 7 days
Clinical measurement of spleen and liver by physical exam	X					X	X
Research Blood Samples		X ⁷			X ^{7,8}		
Adverse Event monitoring	X	X ⁷	X ⁷		X ^{5,7}	X	X
Bone marrow biopsy and aspirate including cytogenetics ⁴	X					X	

Footnotes:

1. To be completed prior to treatment on Day 1. Patient questionnaire booklet must be used; copies are not acceptable for this submission.
2. To be completed on Day 1 of Cycles 4, 5, 7, 8, 10 and 11 at local MD office and faxed to study team
3. Pregnancy test must be completed ≤ 7 days prior to registration
4. ≤ 90 days prior to registration. Repeat at cycle 6 and 12 only.
5. Patients can be contacted by telephone for adverse event assessment when not seen in the clinic.
6. Must be completed at least 90 days prior to registration. Any positive results at baseline will be repeated again every three cycles (Cycle 3, 6, 9, etc).
7. Must be completed prior to treatment.
8. Research blood samples only collected on C1D1, C2D1, and C3D1 prior to treatment.

5.0 Grouping Factor:

Cohort: Cohort 1 (early stage MF) versus Cohort 2 (intermediate-2 or high risk MF)

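### From Cycle 4, Section 4.0 schedules no Day 15 blood count or liver enzymes, even in a cycle in which the P1101 dose has just been raised

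*Combined protocol and SAP*

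**What the plan says.** **Tests.** Section 4.0 places CBC and chemistries (which include AST and ALT) at baseline, on Days 8, 15 and 22 of Cycle 1, in a column headed "Cycle 2 and Cycle 3 Day 15", on Day 1 from Cycle 2 onward, and at discontinuation. For the cycles between clinic visits, footnote 2 reads "To be completed on Day 1 of Cycles 4, 5, 7, 8, 10 and 11 at local MD office and faxed to study team". No column or footnote adds a test when the dose changes.

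**Dosing.** Injections are on Days 1 and 15 at every dose level except the lowest. Section 7.2 starts everyone at 100 mcg, after which the "dose will be titrated up by 50mcg increments to a maximum dose of 300mcg every other week", as tolerated. It gives no interval between steps and no last cycle for a step. The note closing Section 8.0 says that after a dose-reducing event "then the dose will remain lowered for that entire subsequent cycle". If that cycle passes without a further event above grade 2, the investigator may raise the dose again, one level at a time.

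**Action rules.** The first block of Table 8.2 is headed "BASED ON INTERVAL ADVERSE EVENT PRIOR TO DAY 15 EACH CYCLE". It omits the Day 15 dose for a grade 3 platelet fall, grade 4 neutropenia, or a grade 3 rise in ALT or AST.

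**Visits.** The second of the two items numbered 7.3 has the patient return at least every four weeks "through cycle 3 day 1, and then will return every 3 cycles". Section 7.5 allows care by a local doctor after that point "if the patient is tolerating therapy without excessive toxicity at a stable dose level". The first item numbered 7.3 states: "Patients can be instructed in administration techniques and granted treatment independence with nursing staff approval".

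**The concern.** Less testing for a patient on a settled dose is reasonable, and Section 7.5 suggests that this was the intention. But Section 4.0 reduces testing at a fixed cycle, and neither footnote 2 nor the visit rule in 7.3 asks whether the dose is stable. A patient whose dose is raised on Day 1 of Cycle 4 or later follows the same sparse schedule as one who has been on a fixed dose for months.

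Such a patient, possibly one who has already had a dose-reducing toxicity, can self-inject the second higher dose on Day 15 with no scheduled result since the increase. The laboratory changes that should stop that dose can occur without symptoms. The telephone adverse event contact allowed by footnote 5 would not detect them. Section 1.3 says that P1101 had not yet been studied in myelofibrosis, and Section 15.17 lists neutropenia, thrombocytopenia and abnormal liver function for marketed interferons.

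**Working it through.** The plan states no figure for this point, so the check compares the schedule with the dosing rules and counts.

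**1. Cycles with a scheduled Day 15 test.** From Section 4.0: Cycles 1, 2 and 3. The column for Cycle 2 Day 1 and beyond cannot be read as covering later Day 15 doses, because Day 15 of Cycles 2 and 3 has its own column and footnote 2 specifies Day 1.

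**2. Time from a Day 1 increase to the next scheduled test.**
- Cycle 2 or 3: Day 1 to Day 15 is 14 days, with one dose at the new level, because the test precedes the Day 15 dose.
- Cycle 4 or later: Day 1 to the next Day 1 is 28 days, with two doses at the new level (Days 1 and 15).

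**3. Re-escalation, from the note in Section 8.0.**
- Event found by Cycle 2 Day 1: dose lowered for Cycle 2, earliest re-raise Cycle 3. A Day 15 test exists.
- Event found on Cycle 2 Day 15: that dose is omitted and, by the definition of Omit, not made up. The dose is lowered for Cycle 3, and the earliest re-raise is Cycle 4. No Day 15 test exists.
- Any later event: the re-raise also falls in Cycle 4 or later.

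This route does not depend on the titration pace.

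**4. Initial titration.** Number of steps: (300 − 100) / 50 = 4. The pace is not stated, so the following are assumptions.

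| Assumed pace | 150 mcg | 200 mcg | 250 mcg | 300 mcg | Steps in Cycle 4 or later |
|---|---|---|---|---|---|
| One step per dose | C1 D15 | C2 D1 | C2 D15 | C3 D1 | 0 of 4 |
| One step per cycle | C2 D1 | C3 D1 | C4 D1 | C5 D1 | 2 of 4 |

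A slower pace would leave more steps uncovered, but nothing in the plan points to one.

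**5. Other text that might supply a test.** The CBC row says that interval counts may come from a home laboratory, which settles the place and not the time. Sections 15.192 and 15.193 say to monitor liver tests and CBC, without timing. The weekly checks in Table 8.2 apply while a Day 1 dose is held. None of these schedules a Day 15 test from Cycle 4.

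**The case against.** A reader might infer that Table 8.2 and Section 4.0 contradict each other. The documents do not support that. The heading of the Day 15 block says what to do when an event is found; it does not order tests. Section 8.0 calls its rules general guidelines, and they work equally well on an unscheduled result.

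A reader might also infer that much of the dose titration goes unmonitored. That too is unsupported. At one step per dose the patient reaches 300 mcg on Cycle 3 Day 1, exactly where four-weekly visits end and local care may begin, and the last scheduled Day 15 test follows two weeks later. This pace is itself an inference, but it fits the schedule's break point and leaves no initial step uncovered.

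There are further safeguards:
- Local care requires a stable dose under 7.5, so a patient still being raised arguably does not qualify for the route in footnote 2. Section 7.5 also calls for a written list of follow-up tests.
- Re-escalation requires a completed lowered cycle without a further event above grade 2.
- Day 1 tests come before and after each such cycle, so what goes unchecked is one Day 15 dose.

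All of this stands and keeps the point small. It does not close the gap: the stable-dose condition limits who may be seen locally, but gives a patient whose dose is rising no additional scheduled test.

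Nor should the pharmacokinetic data be pressed. Section 15.15 reports more than proportional exposure, but from single doses, and it attributes this partly to variability and few subjects.

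**Conclusion.** The point holds as a limited gap in safety monitoring. From Cycle 4, the Day 15 platelet, neutrophil, ALT and AST rows of Table 8.2 have no scheduled result to act on, even when the dose has risen on Day 1 of that cycle. The interval to the first scheduled test is then 28 days and two doses, compared with 14 days and one dose in Cycles 2 and 3.

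The firmest instance is re-escalation after a toxicity found on Cycle 2 Day 15 or later, which needs no assumption about pace. For initial titration the size is 0 of 4 steps at one step per dose and 2 of 4 at one step per cycle.

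The risk is modest. Day 1 tests continue and physicians may order more. Section 15.17 describes repeated-dose events so far as mild to moderate. The 300 mcg cap is 300 / 540 = 56% of the maximum tolerated dose that Section 1.3 reports in polycythemia vera, also given every two weeks. The plan gives no rate from which to estimate how many toxicities would be missed. The Cohort 2 decision rule and its operating characteristics are unaffected. This is a cheap improvement, not a serious flaw.

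**What to change.** Add one footnote to the CBC and chemistry rows of Section 4.0:

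> From Cycle 4, in any cycle in which the P1101 dose is increased or re-escalated, CBC with differential and AST/ALT are required before the Day 15 dose (home lab allowed); the Day 15 dose is not taken until the result has been reviewed.

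All other cycles from Cycle 4 keep Day 1 tests only. Table 8.2 needs no change: its heading already works for any result that is available, and its requirement of recovery to grade 2 or less before restarting should stay.

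The cost is one routine draw and a short wait for the result, only in cycles with an increase. Initial titration adds 0 or 2 draws per patient under the two paces shown. With the Stage 1 maximum of 19 patients, and if all reach 300 mcg, that is at most 19 × 0 = 0 or 19 × 2 = 38 draws, plus one per re-escalation from Cycle 4. Patients on a stable dose have none. Home-laboratory CBCs are already allowed, and footnote 2 already accepts chemistries from a local office.

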9.0 Ancillary Treatment/Supportive Care

- 9.1 Antiemetics may be used at the discretion of the attending physician.
- 9.2 Blood products and growth factors should be utilized as clinically warranted and following institutional policies and recommendations. The use of growth factors should follow published guidelines of the American Society of Clinical Oncology (42) Update of Recommendations for the Use of Hematopoietic Colony-Stimulating Factors: Evidence-Based, Clinical Practice Guidelines. J Clin Oncol 18(20): 3558-3585, 2000.
- 9.3 Patients should receive full supportive care while on this study. This includes blood product support, antibiotic treatment, and treatment of other newly diagnosed or concurrent medical conditions. All blood products and concomitant medications such as antidiarrheals, analgesics, and/or antiemetics received from the first day of study treatment administration until 30 days after the final dose will be recorded in the medical records.

9.4 Diarrhea: This could be managed conservatively with loperamide. The recommended dose of loperamide is 4 mg at first onset, followed by 2 mg every 2-4 hours until diarrhea free (maximum 16 mg/day).

In the event of grade 3 or 4 diarrhea, the following supportive measures are allowed: hydration, octreotide, and antidiarrheals.

If diarrhea is severe (requiring intravenous rehydration) and/or associated with fever or severe neutropenia (grade 3 or 4), broad-spectrum antibiotics must be prescribed.

Patients with severe diarrhea or any diarrhea associated with severe nausea or vomiting **should be hospitalized** for intravenous hydration and correction of electrolyte imbalances.

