11.0 Treatment Evaluation

Revised International Working Group for Myeloproliferative Neoplasms Research and Treatment (IWG-MRT) as defined by IWG-MRT criteria (Tefferi et al. Blood. 2013)

Table 11.1

Response categories	Required criteria
Complete Remission (CR)	
Bone marrow:* Age-adjusted normocellularity; <5% blasts; \leqGrade 1 myelofibrosis**, AND
 
Peripheral blood: Hemoglobin \geq100 g/L and <UNL; Neutrophil count \geq1 \times 10⁹/L and <UNL;
 
Platelet count \geq100 \times 10⁹/L and <UNL; <2% immature myeloid cells***, AND
 
Clinical: Resolution of disease symptoms; Spleen and liver not palpable; No evidence of EMH

Partial Remission (PR)	
Peripheral blood: Hemoglobin \geq100 g/L and <UNL; Neutrophil count \geq1 \times 10⁹/L and <UNL;
 
Platelet count \geq100 \times 10⁹/L and <UNL; <2% immature myeloid cells***, AND
 
Clinical: Resolution of disease symptoms; Spleen and liver not palpable; No evidence of EMH
 
OR
 
Bone marrow:* Age-adjusted normocellularity; <5% blasts; \leqGrade 1 myelofibrosis**, AND
 
Peripheral blood: Hemoglobin \geq85 but <100 g/L and <UNL; Neutrophil count \geq1 \times 10⁹/L and <UNL;
 
Platelet count \geq50 but <100 \times 10⁹/L and <UNL; <2% immature myeloid cells***, AND
 
Clinical: Resolution of disease symptoms; Spleen and liver not palpable; No evidence of EMH

Clinical improvement (CI)	
The achievement of anemia, spleen or symptoms response without progressive disease or
 
increase in severity of anemia, thrombocytopenia or neutropenia‡

Anemia response	
Transfusion-independent patients: a \geq20 g/L increase in hemoglobin level†
 
Transfusion-dependent patients: becoming transfusion-independent††

Spleen Response §	
A baseline splenomegaly that is palpable at 5-10 cm, below the LCM, becomes not palpable§§, OR
 
A baseline splenomegaly that is palpable at >10 cm, below the LCM, decreases by \geq50%§§
 
A baseline splenomegaly that is palpable at <5 cm, below the LCM, is not eligible for spleen response
 
A spleen response requires confirmation by MRI or CT showing \geq35% spleen volume reduction (optional)

Symptoms response	
A \geq50% reduction in the Myeloproliferative Neoplasm Symptom Assessment Form total symptom score (MPN-SAF TSS)

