See table 11.1 for definitions of anemia response, spleen response and progressive disease. Increase in severity of anemia constitutes the occurrence of new transfusion dependency or a ≥ 20 g/L decrease in hemoglobin level from pre-treatment baseline that lasts for at least 12 weeks. Increase in severity of thrombocytopenia or neutropenia is defined as a 2-grade decline, from pre-treatment baseline, in platelet count or absolute neutrophil count, according to Common Terminology Criteria for Adverse Events (CTCAE) version 4.0. In addition, assignment to clinical improvement (CI) requires a minimum platelet count of $\geq 25,000 \times 10(9)/L$ and absolute neutrophil count of $\geq 0.5 \times 10(9)/L$

Applicable only to patients with baseline hemoglobin of <100 g/L. In patients not meeting the strict criteria for transfusion-dependency at the time of study enrollment (see below), but have received transfusions within the previous month, the pre-transfusion hemoglobin level should be used as the baseline

Transfusion dependency before study enrollment is defined as transfusions of at least 6 units of packed red blood cells (PRBC), in the 12 weeks prior to study enrollment, for a hemoglobin level of <85 g/L, in the absence of bleeding or treatment-induced anemia. In addition, the most recent transfusion episode must have occurred in the 28 days prior to study enrollment. Response in transfusion dependent patients requires absence of any PRBC transfusions during any consecutive “rolling” 12-week interval during the treatment phase, capped by a hemoglobin level of ≥ 85 g/L.

In splenectomized patients, palpable hepatomegaly is substituted with the same measurement strategy

Optional, Spleen or liver responses can be confirmed by imaging studies where a $\geq 35\%$ reduction in spleen volume, assessed by magnetic resonance imaging (MRI) or computed tomography (CT), is required. Furthermore, a $\geq 35\%$ volume reduction in the spleen or liver, by MRI or CT, constitutes a response regardless of what is reported with physical examination.

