18.0 Records and Data Collection Procedures

18.1 Submission Timetables

Initial Material(s) -

Case Report Form (CRF)	Active-Monitoring Phase (Compliance with Test Schedule Section 4.0)
On-Study	
Adverse Event - Baseline	
Measurement - Baseline	
Bone Marrow and Cytogenetics	
Bone Marrow Biopsy Report including Cytogenetics	≤2 weeks after registration
JAK2V617F, BCR/ABL, CALR AND MPL	
Research Blood Submission	
End of Active Treatment/Cancel Notification	Submit ≤2 weeks after registration if withdrawal/refusal occurs prior to beginning protocol therapy
Patient Questionnaire	≤2 weeks after registration – Patient questionnaire booklet must be used; copies are not acceptable for this submission.
Booklet Compliance	≤2 weeks after registration – This form must be completed only if the [name of booklet(s) – or whatever verbiage you want to use to describe the booklet(s)] contains absolutely NO patient provided assessment information.

Test Schedule Material(s)

CRF	Active-Monitoring Phase (Compliance with Test Schedule Section 4.0)	
	At each evaluation during treatment	At end of treatment
Evaluation/Treatment	X	X
Concurrent Transfusion	X	X
Interval Laboratory	X	X
Bone Marrow and Cytogenetics	X ³	
Bone Marrow Biopsy Report including Cytogenetics	X ³	
JAK2V617F, BCR/ABL, CALR AND MPL	X	
Nadir/Adverse Event	X	X
Measurement	X	X
Research Blood Submission	X (see Section 14.0)	
Patient Questionnaire	X ¹	
Booklet Compliance	X ²	
End of Active Treatment/Cancel Notification		X
ADR/AER	At each occurrence (see Section 10.0)	

1. Patient questionnaire booklet **must** be used; copies are not acceptable for this submission.
2. This form must be completed **only** if the booklet contains absolutely **NO** patient provided assessment information.
3. Only required when bone marrow biopsy is performed.

Follow-up Material(s)

CRF	Event Monitoring Phase ¹				
	q. 3 months until PD and/or subsequent treatment ²	At PD ²	After PD and/or subsequent treatment q. 6 mos.	Death	New Primary
Event Monitoring	X	X	X	X	At each occurrence

1. If a patient is still alive 3 years after registration, no further follow-up is required.
2. Submit copy of documentation of response or progression to the MCCC Operations Office, Attention: QAS

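### An anemia response produced by an erythropoietic agent started on study would count as a P1101 primary success, because the Section 11 definition controls for transfusion but not for growth factor support

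*Combined protocol and SAP*

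**What the plan says.** **Permission.** Section 9.2 reads: "Blood products and growth factors should be utilized as clinically warranted and following institutional policies and recommendations". It adds: "The use of growth factors should follow published guidelines of the American Society of Clinical Oncology". The guideline named there is, by its title, about colony-stimulating factors. Erythropoietic agents are not mentioned anywhere; they come in only through the general term for growth factors and through institutional policy. No section asks for a washout or a stable dose, or bars an agent.

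**Scoring.** Table 11.1 defines CI as follows: "The achievement of anemia, spleen or symptoms response without progressive disease or" worsening of anemia, thrombocytopenia or neutropenia. Anemia response has two branches.

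- In transfusion-independent patients it is a rise of at least 20 g/L, with no minimum duration stated. The footnote restricts who can qualify: "Applicable only to patients with baseline hemoglobin of" less than 100 g/L.
- In transfusion-dependent patients it is "becoming transfusion-independent". The footnote explains: "Response in transfusion dependent patients requires absence of any PRBC transfusions during any consecutive" rolling 12-week interval, ending with hemoglobin of at least 85 g/L.

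Section 16.11 counts a best response of CR, PR or CI over all treatment cycles as a success.

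**Recording.** Section 9.3 covers blood products and concomitant medications "received from the first day of study treatment administration until 30 days after the final dose will be recorded in the medical records". The form list in 18.1 includes a "Concurrent Transfusion" form but names no form for concomitant medication or growth factors.

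**The concern.** Transfusion and erythropoietic agents can move the same endpoint, yet the protocol handles only the first. For transfusion it specifies the baseline hemoglobin to use, a transfusion-free window, a patient diary (Appendix V) and a form. For erythropoietic agents there is no counterpart. A transfusion-dependent patient who starts such an agent during treatment and then goes 12 weeks without red cells meets the anemia definition, whatever P1101 did.

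The exposed group matters in cohort 2, where the formal decision is made. Hemoglobin below 10 g/dL is one of three entry routes in 3.10. In Appendix VI it carries 2 points and the other four factors carry 1 each, 4 in total. High risk needs 5 or 6 points, so every High-risk patient has been scored on hemoglobin below 10 g/dL (100 g/L), the threshold for the hemoglobin-rise branch. Some Intermediate-2 patients will be in the same position.

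The Stage 1 rules turn on one patient: 0 of 12 stops the study, while 1 of 12 opens the way to expansion; 3 of 12 leads to considering expansion, while 4 of 12 may lead to a recommendation for further testing.

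**Working it through.** **Inputs from the plan (16.21 to 16.24).** Null success proportion 0.10, target 0.30. Stage 1 has n = 12: stop at 0 successes, favorable at 4 or more, otherwise go on. Stage 2 adds 23 patients and is favorable at 7 or more of 35.

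**Reproducing the plan's table.** With X1 ~ Bin(12, p) and X2 ~ Bin(23, p):

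P(declare) = P(X1 ≥ 4) + Σ (x = 1 to 3) P(X1 = x) × P(X2 ≥ 7 − x)

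- At p = 0.10: 0.0256 + 0.0418 = 0.0674 (plan: 0.07). P(X1 = 0) = 0.90^12 = 0.282 (plan: 0.28).
- At p = 0.30: 0.931 (plan: 0.93).
- Every other cell of the 16.24 table also agrees to rounding. The design arithmetic is sound; the issue is what gets counted as a success.

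**Adding misscored responses.** Let q be the proportion of true non-responders scored as successes only because of an erythropoietic agent. The documents give no value, so q is assumed, with a range of 1% to 10%. True responders are unaffected. When the true proportion is 0.10, the observed proportion is

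p_obs = 0.10 + 0.90 × q

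| q (assumed) | p_obs | P(declare), full design | P(≥ 4 of 12), Stage 1 | P(0 of 12), Stage 1 |
|---|---|---|---|---|
| 0 | 0.100 | 0.067 | 0.026 | 0.282 |
| 1% | 0.109 | 0.094 | 0.034 | 0.250 |
| 2% | 0.118 | 0.127 | 0.044 | 0.222 |
| 5% | 0.145 | 0.254 | 0.083 | 0.153 |
| 10% | 0.190 | 0.519 | 0.180 | 0.080 |

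**What such a q would take.** Write q as the share eligible for anemia response × the share starting an agent × the share responding because of it. Assumed values of 0.5 × 0.1 × 0.2 give 0.01, and 0.75 × 0.3 × 0.4 give 0.09. These only show which combinations correspond to the range; none of the factors is in the documents.

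**The case against.** The best counter-case is that the permission is ordinary supportive care, that erythropoietic agents are never named, and that the frequency is unknown. To be misscored, a patient must be eligible for anemia response, start or increase an agent, respond because of it, pass every CI guard, and have no spleen or symptoms response that would have made the patient a success anyway. The criteria are also taken from a published consensus, so changing them costs comparability. The Stage 1 wording is permissive, and 16.25 lets quality and duration of response weigh in any termination decision. All of this limits the size of the problem and argues for reporting both versions. None of it supplies a scoring rule.

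Three stronger readings are tempting, and the documents do not support them.

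- *A reader might infer that G-CSF could also manufacture a success.* It cannot. CI needs an anemia, spleen or symptoms response, and neutrophils act only as a guard. CR and PR further require neutrophils below the upper normal limit, under 2% immature myeloid cells (under 5% after splenectomy), symptom resolution, and a non-palpable spleen and liver. G-CSF can at most keep a patient who has another response component from failing a neutrophil condition.
- *A reader might infer that affected patients could never be identified.* Section 9.3 puts concomitant medications in the medical record, Stage 1 has at most 19 patients, and patients return to the study site at least every 3 cycles. Chart review is feasible. The accurate statement is that no form named in 18.1 is dedicated to growth factors; the fields on the listed forms are not shown. Recording under 9.3 also starts at first dose, so baseline use would have to come from the treatment history.
- *A reader might add 5 or 10 percentage points to the null and read 0.28 and 0.58 from the 16.24 table.* That assumes every affected patient would otherwise have failed. With 5% or 10% as the rate among non-responders, the figures are 0.254 and 0.519.

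**Conclusion.** The point holds for erythropoietic support and the anemia response. As written, Sections 9.2, 11 and 16.11 together credit P1101 with an anemia response that another drug produced, and the bias runs only toward success. The design is sensitive to it: an assumed 2% of non-responders misscored is enough to take the full-design false-positive probability from 0.067 to 0.127. The full-design figures apply only if the study is amended into Stage 2. For Stage 1 alone the shift is smaller, with P(≥ 4 of 12) at 0.034 to 0.180 instead of 0.026 and P(0 of 12) at 0.250 to 0.080 instead of 0.282.

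The gap itself can be read from the text. Its size rests on the assumed q, on independent binomial outcomes, and on misscoring confined to true non-responders. Whether the cited consensus paper restricts growth factors cannot be checked here; the criteria as set out in Section 11, to which 16.11 refers, do not.

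**What to change.** Leave care under 9.2 unchanged and change only scoring, data capture and reporting, before responses are read.

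1. In Sections 11 and 16.11, state that an anemia response does not count toward CI if an erythropoiesis-stimulating agent was started or increased after baseline and was in use during the 12-week window, or at the hemoglobin reading, that defines the response. A spleen or symptoms response in the same patient still counts.
2. Add growth factor name and start and stop dates, including use at baseline, to an existing form in 18.1. Until then, take on-study use from the medical record kept under 9.3.
3. Report the success rate under this rule and also under the criteria as they now stand, so that results remain comparable with other studies.
4. Flag responses with G-CSF-supported neutrophil counts in that sensitivity report. Do not rescore them: a rescoring rule would need a washout interval and a decision on how to treat the patient meanwhile, and the gain is small.

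The cost is an amendment to two sections, a few form fields, a second reported rate, a small departure from the consensus criteria, and a slightly lower observed success rate. The last includes any patient who responded to P1101 while also receiving a newly started agent.
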